3 INTRODUCTION

3.1 Background information

The World Health Organization (WHO) estimates that lower respiratory tract infection (LRTI), including pneumonia, is the third most common cause of death worldwide. LRTI caused 3.1 million deaths in 2012 [23].

Pneumonia is an acute illness characterized by symptoms and signs of lower respiratory tract infection, with new radiographic shadowing for which there is no alternative explanation. Community-acquired pneumonia (CAP) is pneumonia acquired outside a hospital or long-term care facility and being diagnosed within 48 hours of hospital admission [14].

Evidence suggests CAP is most commonly caused by bacterial infection [14].

Streptococcus pneumoniae (the most common etiologic agent), nontypeable Haemophilus influenzae, and the atypical organisms (i.e., Mycoplasma pneumoniae, Chlamydia pneumoniae, and Legionella pneumophila) are the most frequently isolated pathogens from patients of any age who require hospitalization for CAP [17] [20].

Increasing resistance to a variety of antimicrobial agents has been documented in *S pneumoniae* and is common in *H influenzae* as well. In addition to penicillin resistance (penicillin-intermediate S. pneumonia - PISP, or penicillin-resistant S. pneumonia - PRSP), isolates of *S pneumoniae* have demonstrated increasing resistance to other classes of antimicrobials, including macrolides, tetracyclines, trimethoprim-sulfamethoxazole (TMP-SMX), and fluoroquinolones [8] [9]. Surveillance studies indicate that the prevalence of drug-resistant *S.pneumoniae* (DRSP) continues to increase worldwide [8].

The basic problem of resistance in *H. influenzae* species is defined by ampicillin as the resistance marker. The resistance of *H. influenzae* to ampicillin may occur due to production of β -lactamases (TEM-1, TEM-2, and with lower frequency ROB-1) or as a result of mutations in the *ftsI* gene that cause alterations in the amino acid sequences of penicillin-binding protein 3 (PBP3) in so called β -lactamase negative ampicillin-resistant (BLNAR) strains. Strains producing β -lactamases remain susceptible to amoxicillin/clavulanate; however, clavulanate is inactive against BLNAR strains, so such strains are resistant to amoxicillin/clavulanate. BLNAR strains are also resistant to ampicillin–sulbactam, cefaclor, and cefuroxime. Both mechanisms of resistance, i.e., β -lactamase production and mutations in the *ftsI* gene, are present in β -lactamase positive amoxicillin–clavulanic acid resistant (BLPACR) strains [2] [12].

The number of necrotizing or cavitary pneumonia may be caused by methicillin-resistant *Staphylococcus aureus* (MRSA) [19]. MRSA has been a major cause of nosocomial infections, and thus is alternatively called hospital-acquired MRSA (HA-MRSA). In addition, another class of MRSA has become a major concern worldwide as an emerging pathogen in the community. This new class of MRSA is called community-acquired MRSA (CA-MRSA) [22]. MRSA is resistant to b-lactam antibiotics, including penicillin and cephalosporins. Compared with nosocomial MRSA, CA-MRSA species are generally more susceptible to antibiotics, including trimethoprim–sulfamethoxazole, rifampin, quinolones, and clindamycin, though resistance to clindamycin may be selected [4]. Published data has suggested that CA-MRSA was not a frequent cause of community-acquired pneumonia (CAP), although with increasing incidence over the past few years the

CONFIDENTIAL Page 23 of 88

frequency of CA-MRSA CAP can be estimated to be between one in 200 and one in 2000 cases of CAP [13].

Initial antimicrobial treatment for patients with CAP should provide appropriate coverage against the most common causative organisms, including resistant strains [17].

The European Respiratory Society (ERS) and the European Society for Clinical Microbiology and Infectious Diseases (ESCMID) recommends that initial empirical treatment for hospitalized non-intensive care unit (non-ICU) patients with CAP should be provided with following antibiotics (with one of proposed regimens): aminopenicillin with or without macrolide; aminopenicillin/b-lactamase inhibitor \pm macrolide; non-antipseudomonal cephalosporin; cefotaxime or ceftriaxone with or without macrolide; levofloxacin; moxifloxacin; penicillin G with or without macrolide [21].

The American Thoracic Society and the Infectious Diseases Society of America (ATS/IDSA) consensus guidelines on the management of CAP in adults recommend that the standard empirical regimen should routinely cover the 3 most common pathogens that cause severe CAP, all of the atypical pathogens, and most of the relevant Enterobacteriaceae species. ATS/IDSA recommends treating CAP with a respiratory fluoroquinolone or a b-lactam plus a macrolide for hospitalized non-ICU adult patients [11].

According to Russian guidelines on the management of CAP in adults monotherapy with respiratory fluoroquinolones (levofloxacin; moxifloxacin) is an alternative to combination of blactam plus a macrolide [1].

In summary, fluoroquinolones are highly active and efficacious against respiratory pathogens [21] and in some cases should be used as first-line agents [18].

Although respiratory pathogens (e.g., Moraxella catarrhalis, Haemophilus influenzae, and Streptococcus pneumoniae) are generally susceptible to quinolones, resistance does occur, it has been reported in localized outbreaks [10], and is associated with clinical failure [6] [7]. Some CAMRSA clones have become fluoroquionlone resistant [22].

The problem of fluoroquinolone resistance has brought great challenge into clinical practice. Therefore, the development of newer quinolone compounds with greater activity and less resistance is urgently required [15].

3.2 Investigational products

Nemonoxacin is a novel non-fluorinated quinolone (NFQ) and will be investigated as an investigational product in this clinical study. Nemonoxacin inhibits bacterial DNA gyrase, a key topoisomerase involved in the formation of bacterial DNA supercoils [28].

Nemonoxacin was first developed by Procter and Gamble Pharmaceuticals (Cincinnati, OH, USA) and completed the Phase IA single-dose escalation studies in 2004. Thereafter, it was authorized to TaiGen Biotechnology Co, Ltd (Taipei, Taiwan) for worldwide clinical trials and further development [15]. TaiGen Biotechnology Co., Ltd. licensed Russian pharmaceutical company R-Pharm JSC exclusive rights to develop and register Nemonoxacin in the Russian Federation, other members of the Commonwealth Independent States (CIS) countries and Turkey (http://r-pharm.com).

The drug is available in intravenous (i.v.) and capsules formulations. Nemonoxacin capsules has already been approved in Taiwan and China for treatment of CAP. Intravenous formulation has passed phase II of clinical studies and phase III clinical study is ongoing in China.

CONFIDENTIAL Page 24 of 88

Tavanic® (levofloxacin) is an approved fluoroquinolone, which will be used as a comparator in this clinical study.

Levofloxacin is the optically active L-isomer of ofloxacin and acts on the DNA-DNA-gyrase complex and topoisomerase IV. Levofloxacin is indicated in adults for the treatment of community-acquired pneumonia, skin and soft tissue infections, uncomplicated and complicated urinary tract infections including acute pyelonephritis, chronic bacterial prostatitis, etc. The CAP indication is approved for both tablets and i.v. formulations of levofloxacin.

3.3 Preclinical and clinical studies of Nemonoxacin

Below there is brief information on the results of preclinical and clinical studies. Detailed information is presented in Investigational Brochure.

Nemonoxacin was investigated under the research number "TG-873870". The malate salt hemihydrate of TG-873870, "TG-875649", was determined to be conducted in the initial clinical studies; dosing was adjusted to reflect the clinical dosage of anhydrous free base, TG-873870.

3.3.1 Preclinical studies of Nemonoxacin

3.3.1.1 In vitro studies on antibacterial activity of nemonoxacin

Nemonoxacin had broad-antibacterial spectrum *in vitro*. It exhibited strong antibacterial activity against penicillin-sensitive or penicillin-intermediate, or penicillin-resistant *S. pneumoniae* (PSSP, PISP, PRSPA), some gram-negative bacteria (e.g., *M. catarrhalis*, *H. influenzae*, etc.), and atypical pathogens (such as *L. pneumophila*, *M. pneumoniae* and *C. pneumoniae*). In addition, this drug also showed good antibacterial activity against community-acquired methicillin-resistant *S. aureus* (CA-MRSA) and drug-resistant *S. pneumoniae* (DRSP) [28]. In case of respiratory pathogens nemonoxacin had the same or superior activity to marketed fluoroquinolones [5][28].

In accordance to the drug resistance tests on Nemonoxacin it was shown that mutation site of the drug in the quinolone resistance-determining regions (QRDRs) was different from other quinolones (mutation generally occurred in *gyrA* and *parC*) [28].

3.3.1.2 Efficacy of nemonoxacin in pulmonary model of infection

The *in vivo* antibacterial efficacy of nemonoxacin was evaluated in a mouse pulmonary model of infection by *Streptococcus pneumonia* and in a mouse pulmonary model of infection by penicillin-resistant *S. pneumoniae* and *K. pneumoniae*. During the first study nemonoxacin significantly reduced the amount of viable bacteria in lungs and blood samples at all dosage levels when compared to vehicle-treated controls and protected from death in 100% cases. Moreover nemonoxacin was more effective than moxifloxacin at the same dosage levels. In the second study nemonoxacin also significantly reduced the viable bacteria counts of penicillin-resistant *S. pneumoniae* in lungs when compared to vehicle-treated controls and had slightly higher efficacy than levofloxacin. Against the *K. pneumoniae* infections, oral administration of nemonoxacin showed a significantly reduction in bacteria counts when compared to vehicle-treated controls but the drug had lower efficacy than levofloxacin [28].

CONFIDENTIAL Page 25 of 88

3.3.1.3 Animal pharmacokinetics and metabolism

Nemonoxacin absorption was nearly complete after single oral dosing in dogs and monkeys (bioavailability of 80% in monkeys and 100% in dogs), while bioavailability was lower (~30%) in rats. Food decreased the bioavailability by up to 77% in monkeys.

Protein binding to mouse, rat, rabbit, dog, monkey and human plasma was low (ranging from 12 to 48%) over the concentration range of 0.1 to 1000 μ g/mL, indicating little potential for protein binding-based drug interactions.

After single-dose intravenous infusion (10 mg/kg) or oral gavage administration (30 mg/kg) of Nemonoxacin to rats, the drug was distributed to body immediately; the concentrations of Nemonoxacin in kidney, liver, submandibular gland, small intestine, lung and spleen were the higher, followed by heart, muscle, large intestine, pancreas and bladder. The concentrations of nemonoxacin in brain and fat were relatively lower. There was a significant difference between ovary gonads and testicles. For both administration routes, drug was distributed similar in body.

Monkey and human hepatocytes did not metabolize nemonoxacin. The rat hepatocytes produced one metabolite (a glucuronide conjugate) but the extent of metabolism was low (<5% of total drug) [28].

3.3.1.4 Toxicological studies

The in vitro genotoxicity (mutagenicity) was considered to be related to its mechanism on inhibition of DNA gyrase by the drug. In mice micronucleus tests and rat unscheduled DNA synthesis tests, animals administered with nemonoxacin at a dose up to 2000 mg/kg did not produce in vivo genotoxicity. The drug had no potential to cause hemolytic effect in *in vitro* hemolysis test with rabbit erythrocytes.

In repeated dose toxicity studies renal tubular effects were observed at ≥ 20 mg/kg following 7 days of dosing, but these effects were not observed at up to 1000 mg/kg (AUC ≈ 130 h* μ g/mL) following 1 month of dosing in rats, or up to 500 \rightarrow 300 mg/kg (AUC ≈ 680 h* μ g/mL) in monkeys. This likely represents the large capacity of the kidney to adapt to the effect.

In the 1-month monkey study, watery stools were observed at a dose of 30 mg/kg (AUC = 60 h* μ g/mL), emesis, sinus bradycardia, and increased urine protein at a dose of 100 mg/kg (AUC = 230 h* μ g/mL), and QRS widening, decreased activity, ptosis, pale skin, dilated pupils, and thymic atrophy at a dose of 500 mg/kg (AUC = 690 h* μ g/mL). There was a dose-dependent prolongation of mean QTc and a reduction of the mean heart rate (prolonged R-R interval) for the high dose group (500/300 mg/kg) at 3 hours post dose on Days 5 and 26. The mean QTc was mildly prolonged in the female monkeys and the mean heart rate reduced for the mid dose group (100 mg/kg). The mean QTc and heart rate recovered by the subsequent 24-hour timepoint for both groups. These changes were attributed to the administration of TG-875649 (nemonoxacin malic acid salt, hemihydrate).

In a 28-day dog study, QTc prolongation was observed in dogs treated with second dose of 100 mg/kg at 1 hour post-dose, but this sign was not seen at 24 hour post-dose. No ECG change was noted after the last dose administration.

A battery of safety pharmacology studies was conducted to assess the effect of TG-873870 on the central nervous system (CNS), cardiovascular system, respiratory system, gastrointestinal (GI) system, and renal system. Based on the results of the studies it was demonstrated that TG-873870 had effects on the CNS, GI systems and on cardiac electrophysiology, which were

CONFIDENTIAL Page 26 of 88

consistent with the known pharmacology of quinolones. The hERG and Purkinje findings suggest the possibility of QTc prolongation in man. Mild effects were also seen at the high dose (1000 mg/kg) in some CNS (decreased SMA) and GI (decreased gastric motility) studies.

Nemonoxacin did not elicit cutaneous phototoxicity when administered orally either once or repeatedly; did not produce systemic hypersensitive reactions during active systemic anaphylaxis test. In the bone/cartilage studies in juvenile dogs administered nemonoxacin at 10, 20, or 40 mg/kg/day for 4 weeks, the microscopic changes were noted in 2/3 males and 3/3 females of the 40 mg/kg/day dose group, the changes were graded minimal to moderate in severity and characterized by degeneration/necrosis with or without horizontal clefting and/or erosion of the articular cartilage. The nature and distribution (targeting the weight bearing area and middle zone of the proximal and distal femur) of these microscopic changes were compatible with quinolone-induced arthropathy/chondrotoxicity. No apparent changes were seen after 13 weeks recovery, suggesting a complete reversibility of the changes [28].

3.3.1.5 Interaction with cytochrome P450

Human primary hepatocytes were used to test the inducing potential of nemonoxacin. Nemonoxacin showed no significant induction or inhibition of CYP 1A2, 2B6, 2C8, 2C9, 2C19 and 3A4 at concentration up to $100 \,\mu$ g/mL [28].

3.3.2 Clinical studies of nemonoxacin

At this time thirteen clinical studies of nemonoxacin, oral capsules, with a total of more than 870 subjects have been completed in U.S., China, South Africa and Taiwan. Five clinical studies of nemonoxacin, solution for infusion, have been already conducted in more than 380 subjects.

3.3.2.1 Phase I clinical trials

During a randomized, double-blind, placebo-controlled, parallel-design, single ascending dose study (#2003107) carried out in the USA the safety, tolerability, and pharmacokinetics of orally administered nemonoxacin in healthy male and female volunteers were investigated. Fifty six subjects were enrolled in the study. Healthy volunteers were randomized to the nemonoxacin group and the control (placebo) group at a ratio of 3:1. Nine escalating dose cohorts, i.e. 25 mg, 50 mg, 125 mg, 250 mg, 500 mg, 1000 mg, 1500 mg, 2000 mg and 2500 mg, were planned. However, because of the AEs (pruritus and erythema), dose escalation was stopped after 1500 mg dose. Therefore, 1500 mg was defined as the maximum tolerated dose. There were no significant laboratory and ECG abnormalities and also no vital signs abnormalities. Nemonoxacin was rapidly absorbed after oral administration in the fasted state, with peak plasma concentrations attained within 1 to 2 hours post-dose. The mean terminal exponential half-life $(T_{1/2})$ was approximately 10 hours over the 25 mg to 250 mg dose range and increased to approximately 15 hours at higher doses. The mean renal clearance rate was approximately 0.09 L/h/kg; the mean oral clearance rate was approximately 0.22 L/h/kg; and the mean terminal volume of distribution was 3.8 L/kg. The mean urinary excretion was approximately 45% of the administered dose over the 25mg to 1500 mg dose range and 75% of the urinary excretion occurred within the first 24h after drug administration. In addition, the mean plasma protein binding of approximately 16% was observed over the concentration range of 141 ng/mL to 4270 ng/mL [28].

CONFIDENTIAL Page 27 of 88

The safety, tolerability and pharmacokinetics of multiple orally administered doses of nemonoxacin were investigated during a randomized, double-blinded, placebo-controlled, escalating, multiple-dose study (#TG-873870-01) conducted in the USA in healthy volunteers. A total of 46 subjects were enrolled in the study. Each subject received an assigned dose of the study drug or the placebo once daily for ten days. Five dose groups, e.g. 75 mg, 250 mg, 500 mg, 750 mg and 1000 mg, were studied. Each of the 75 mg and 250 mg dose groups consisted of 8 subjects. The ratio of the investigational drug to placebo was 3:1 (6 active, 2 placebo). Each of the 500 mg, 750 mg and 1000 mg dose groups consisted of 10 subjects. The ratio of the investigational drug to placebo was 4:1 (8 active, 2 placebo). There were no apparent differences in laboratory test, ECG intervals, ECG morphology, vital signs measurement and physical examination findings during the study. With the exception of changes in serum amylase and serum lipase in one subject each, there were no clinical laboratory findings of potential clinical concern during the study. There was rapid absorption of nemonoxacin following oral administration in the fasted state, with peak plasma concentrations attained within 1 to 2 hours post-dose. Half-life ranged from approximately 7 to 8 hours after single dose administration of 75 mg - 1000 mg. The half-life appeared to increase after repeated administration for 10 days (ranged from approximately 18-23 hours). The presence of food led to decrease in both C_{max} and AUC (C_{max} and AUC_{0-24h} decreased by approximately 46% and 27% respectively in the fed state) and a 3-hour delay in median T_{max} [28].

A phase I clinical study of intravenous administration of Nemonoxacin malate sodium chloride injection was carried out in China and consisted of four parts (TG-873870-C-2: part A, B, C-1 and C-2). During the part A of study the tolerability of intravenous Nemonoxacin malate injection was investigated. To explore the safe dose by evaluating the safety and tolerability of eight dose levels of nemonoxacin (25, 50, 125, 250, 500, 750, 1000 and 1250 mg) the drug was given as single intravenous dose in Chinese healthy subjects. A total of 92 subjects were assigned into 12 groups with equal numbers of male and female. The tolerated-dose study of the nemonoxacin indicated that the tolerated-dose ranged from 25 mg to 1250 mg and the maximum dose was 1250 mg. The most common drug-related AE was local reaction at administration sites (27/68) and skin rash with or without pruritus (13/68) All AEs were mild and transient, and recovered spontaneously during the administration or shortly after administration. No important or serious AEs that led to study discontinuation and clinical significant change in ECG was observed. As for the laboratory tests, no drug related hyperglycemia or hypoglycemia occurred. The infusion rate of the drug ranged from 0.42 mg/min to 8.33mg/min. The occurrence of skin rash was more common with infusion rate of 8.33 mg/min (3 subjects each in 500 mg and 750 mg group), and all other infusion rates (0.42 mg/min to 5.56 mg/min) were tolerated well.

Part B of the trial evaluated the pharmacokinetic profiles of single-dose nemonoxacin malate sodium chloride injection at 250, 500, and 750mg in healthy Chinese volunteers (see Brochure for details).

During the part C-1 (500 mg and 750 mg doses were investigated) and C-2 (500 mg, 650 mg and 750 mg doses were investigated) of study the tolerability and pharmacokinetics of the multidose continuous intravenous infusion of nemonoxacin malate was investigated. During these studies there were no serious AEs and clinical significant change in ECG. In the C-1 study after the multiple intravenous infusions of nemonoxacin C_{max} on day 10 (steady state) in the 500mg and 750mg group was $9.600\pm1.838~\mu g/mL$ and $11.039\pm2.177~\mu g/mL$ respectively. AUC $_{0-t}$ (for 500 mg group: 22.5h; for 750 mg group: 21.75h) was $44.03\pm8.62~\mu g.h/mL$ and $65.82\pm10.78~\mu g.h/mL$ respectively. Statistical analysis revealed no cumulative effect in both groups after administration for consecutive 10~days [28].

CONFIDENTIAL Page 28 of 88

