3.3.2.2 Phase II clinical trials

A randomized, double-blind, comparative, multi-center study (#TG-873870-02) of the safety and efficacy of oral nemonoxacin versus oral levofloxacin in adult patients with CAP was carried out in 19 study centers in South Africa and Taiwan. A total of 265 subjects were enrolled and randomized in the study: 86 patients in the nemonoxacin 750 mg group, 89 in the nemonoxacin 500 mg group and 90 in the levofloxacin 500 mg group. Patients received therapy once daily for 7 days. The study revealed that 750 and 500 mg nemonoxacin had similar clinical efficacy when compared with 500 mg levofloxacin once daily for 7 days. The safety profile of nemonoxacin was also similar to that of levofloxacin and it was consistent with the favorable safety results of nemonoxacin in previous phase I studies [28].

Efficacy and safety of Nemonoxacin malate sodium chloride injection versus Moxifloxacin hydrochloride sodium chloride injection in the treatment of moderate to severe adult CAP were evaluated during a multi-center, randomized, double-blind, parallel, controlled, phase II study. Patients received either 500 mg nemonoxacin, 650 mg nemonoxacin, or comparator drug moxifloxacin 400 mg once a day for 7 to 14 days. A total of 207 subjects were randomly enrolled in 30 research centers: 69 subjects were in the nemonoxacin 500mg group, 68 subjects were in the nemonoxacin 650 mg group and 70 subjects were in the control group (moxifloxacin 400mg). Nemonoxacin had shown similar clinical efficacy, microbiological efficacy, and overall efficacy when compared with moxifloxacin hydrochloride sodium chloride injection once a day for 7 to 14 days. The AEs reported during the study were mostly mild, transient, and tolerated by most patients. The main drug-related AEs in patients who received nemonoxacin were local reactions at the infusion site. The main drug-related laboratory abnormalities were elevated liver transaminases without bilirubin elevation [24].

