8.9 Treatment compliance

Intravenous treatment will be administered under the supervision of investigational site personnel and date, start and stop time, volume (mL) of each infusion will be documented in the eCRF. Oral dosing will be also performed under the supervision of investigational site personnel. The total amount of oral dosing completed (capsules count) as well as dose administered, date and time of dosing will be recorded in the eCRF.

Patients should be informed that compliance with taking all oral medication as instructed is imperative.

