Switch to oral therapy (first oral dose)				X ¹²				
Daily oral therapy (until					XXX			

	Visit 1 ¹			Visit 2 ¹		Visit 3 ¹	Visit 4 ¹	Visit 5 ¹
Study procedures/assessments	Day 1 ²		Days 2-3(7)	Day 4(8)	Days 5(9)-7(14)	Within 1-2 days after the last dose ³	Within 7-9 days after the last dose ⁴	Within 21-23 days after the last dose
	Screening procedures	Randomization and initiation of therapy	Continuation of intravenous therapy	Switch to oral therapy	Continuation of oral therapy	End of treatment visit	Test of cure visit	Long-term follow up visit
Day 7-14 of the study)								
Compliance check		X	XXX	X	XXX			
Other								
Prior/concomitant medication and therapies	X	X	XXX	X	XXX	X	X	X

X – All procedures should be performed during one day.

XXX – All procedures should be performed every day during mentioned period of time.

- 1 All procedures of Visit 1 and Visit 2 will be performed during patient's hospital stay. All procedures of Visit 3 and Visit 4 can be performed at outpatient department. Visit 5 will be conducted as a telephone contact.
- ² The maximum duration is 24 hours after the signing of informed consent.
- ³ The Visit should be conducted at least 24 hours after the last dose of the study drug.
- ⁴ All the efforts should be made to conduct this visit (Visit 4) 7 days after the end of treatment.
- ⁵ The procedure should be done before dosing.
- ⁶ On Day 1 of Visit 1 the procedure should be done 2 hours ±30 minutes after the infusion of second solution is finished. On Days 2-3(7) of Visit 1 the procedure should be done before dosing and 2 hours ±30 minutes after the infusion of second solution is finished. At Visit 2 the procedure should be done before dosing and 2 hours ±30 minutes after capsules intake.
- ⁷ At screening, during the study selection criteria assessment, the Investigator may use laboratory test results obtained at the laboratory of the investigational site within 24 hours of study enrollment (signing of the Informed Consent Form) if he / she considers that available data are sufficient to permit a decision on whether the subject meets the selection criteria. In this case, another blood sampling procedure has to be conducted in the period from the signing of the Informed Consent Form to the start of treatment in order to evaluate all other laboratory parameters that have to be determined on Day 1 in accordance with the study protocol.

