- Documentation of AEs/SAEs occurred after the first IMP administration
- Compliance check
- Assessment of concomitant medication and therapies
- Blood sample collection for PK (via venous catheter): pre-dose, 0 h, 0.5 h (±3min), 2.5h (±5min), 4h (±5min), 6h (±10min), 12h (±15min), 16h (±15min) and 22.5h (±15min) after the end of first infusion (**only for investigational sites defined by the Sponsor**). The last blood sampling for PK (22.5h after the end of the first infusion) should be conducted prior to the IMP infusion on Day 2.

Continuation of intravenous therapy (Days 2-3(7))

All of the following procedures should be performed on each day of Days 2-3(7) of the study:

- Physical examination before dosing
- Assessment of vital signs before dosing
- Intravenous therapy with IMP
- Assessment of vital signs 2 hours ± 30 minutes after the second infusion is finished
- Documentation of AEs/SAEs
- Compliance check
- Assessment of concomitant medication and therapies

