12.7 Safety evaluation

Safety evaluation will include assessment of AEs, vital signs, ECG, physical examination data and laboratory assessment in the safety population. All safety statistical analyses will be performed descriptively.

AEs/ADRs/SAEs will be analyzed descriptively, the evaluation of adverse events will comprise various frequency tabulations by system organ class and preferred term coded according to MedDRA. The AEs will be will be tabulated for each treatment group separately on a patient basis (counting each preferred term once per patient). Descriptive statistics will be also tabulated by relation to study drugs and severity by treatment group. The tables for AEs will present the number of patients with an event within each preferred term as a percentage of the number of treated patients. The number of events within each preferred term will also be reported. For each patient and each adverse event, the worst severity category recorded will be used in the by-severity summaries. The worst causality category (most related to treatment) will be used in the by-causality summaries.

Blood count, biochemistry and urinalysis data as well as change from baseline in laboratory data will be tabulated descriptively by treatment group and by visit. Frequency tables of laboratory shifts with respect to the reference range will also be presented. Clinically relevant abnormalities will be listed individually.

Vital signs data and change from baseline values will be summarized descriptively by treatment group and by visit.

The baseline and postbaseline ECG as well as physical examination data will be summarized descriptively by visit and by treatment group.

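### No skin or infusion-site check follows an i.v. infusion, and Section 12.7 plans no grouped by-arm count of infusion-site reactions or rash, the commonest known i.v. reactions

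*Combined protocol and SAP*

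**What the plan says.** **Known reactions.** Section 3.3.2.1 reports, for single i.v. doses in healthy volunteers: "The most common drug-related AE was local reaction at administration sites (27/68) and skin rash with or without pruritus (13/68" of subjects. On their course it says: "All AEs were mild and transient, and recovered spontaneously during the administration or shortly after administration". Section 3.3.2.2 reports the same leading problem in pneumonia patients given the i.v. form: "The main drug-related AEs in patients who received nemonoxacin were local reactions at the infusion site".

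**Examination schedule.** Skin is one item of the physical examination (Section 10.3.1). For Days 2-3(7), Section 9.2.1 lists "Physical examination before dosing", and footnote 5 of Table 9-1 says of the marked procedures: "The procedure should be done before dosing". On Day 1 the examination belongs to screening. After the infusions, the only scheduled assessment is vital signs, about two hours after the second bag. Section 10.3.2 lists these as pulse, blood pressure, respiratory rate and temperature.

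**AE recording.** AEs are documented on every i.v. day, whether observed by staff or reported by the patient (Sections 9.2.1, 10.3.7, 11.2). Site staff supervise the infusions, and "date, start and stop time, volume (mL) of each infusion will be documented in the eCRF" (Section 8.9). That section names no tolerability item.

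**AE analysis.** Section 12.7 tabulates AEs by treatment group, by system organ class and preferred term, on a patient basis ("counting each preferred term once per patient"). Event numbers, severity and relationship are added. Under Section 12.1, the safety population needs one full dose of nemonoxacin or Tavanic plus a safety evaluation.

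**The concern.** Comparing the safety of nemonoxacin with that of Tavanic is a secondary objective (Section 4.2), and the i.v. form is the less established of the two nemonoxacin products (Section 3.2). The reactions that the background ranks first are brief and mild. The schedule puts no skin or site inspection in the period when they would be visible, so sites may differ in how many they record.

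The analysis adds a second gap. A reader of the report will want to know how many patients per arm had any infusion-site reaction, and how many had any rash or pruritus, while on i.v. treatment. Section 12.7 does not promise either number, and preferred-term rows cannot be added up to give it. The population rule adds a third: a patient who stops during the first infusion because of a reaction may not appear in the table at all.

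**Working it through.** There is no stated figure to reproduce here. The check sets the schedule against the known time course, then asks what the planned tables can deliver.

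**1. Background rates (Section 3.3.2.1).** Exact 95% intervals:
- Local reaction: 27/68 = 39.7% (28.0% to 52.3%).
- Rash with or without pruritus: 13/68 = 19.1% (10.6% to 30.5%).

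Applied to 171 patients, these give 171 × 27/68 ≈ 68 and 171 × 13/68 ≈ 33. That is an extrapolation from healthy volunteers, single doses of 25 to 1250 mg and infusion rates of 0.42 to 8.33 mg/min. In this trial the rate is 500/110 = 4.55 to 500/90 = 5.56 mg/min. Rash was more common at 8.33 mg/min, while "all other infusion rates (0.42 mg/min to 5.56 mg/min) were tolerated well". So 19.1% may overstate rash here.

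**2. Timing of scheduled looks.**
- Pre-dose examination: with dosing every 24 h, the gap from the end of the previous nemonoxacin bag is 24 h minus 90 to 110 min, about 22.2 to 22.5 h. The last PK sample, 22.5 h after the first infusion and just before the Day 2 dose, agrees.
- Post-infusion vital signs: the second bag takes at least 60 min and the assessment follows 90 to 150 min after it. That is at least 60 + 90 = 150 to 60 + 150 = 210 min after the nemonoxacin bag ends, and 90 to 150 min after a Tavanic bag ends. No skin or site item is attached.

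No scheduled skin or site look falls during an infusion or shortly after it.

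**3. What preferred-term rows can tell.** If n₁, …, n_k patients appear in k related rows, the number with at least one of the terms lies anywhere between the largest nᵢ and the sum. Illustration: take the 68 patients above and assume four related terms. Four rows of 68/4 = 17 patients fit 68 different patients (68/171 = 39.8%) or the same 17 patients four times (17/171 = 9.9%). The system organ class row does not settle this, because a class is wider than one reaction and the documents do not list its content.

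**4. Denominator.** Section 12.2 counts any incomplete infusion as a missed dose. A patient whose first and only infusion was cut short has therefore had no complete dose and falls outside the safety population. The bag order also puts the threshold at different points: nemonoxacin is complete at the end of the first bag, Tavanic only at the end of the second. The documents do not allow the number of such patients to be estimated. It may be nil, since Phase I reports no important or serious AE leading to discontinuation.

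**5. What incomplete capture would do (all assumed).** Suppose the true nemonoxacin rate is 27/68, the Tavanic rate is half of it, and capture c is equal in both arms. With p₁ = c × 27/68 and p₂ = p₁/2, the half-width is 1.96 × √[p₁(1−p₁)/171 + p₂(1−p₂)/171].

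| Capture c | Nemonoxacin | Tavanic | Difference, points | 95% half-width |
|---|---|---|---|---|
| 100% | 39.7% | 19.9% | 19.9 | 9.5 |
| 75% | 29.8% | 14.9% | 14.9 | 8.7 |
| 50% | 19.9% | 9.9% | 9.9 | 7.5 |
| 25% | 9.9% | 5.0% | 5.0 | 5.5 |

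With equal true rates, equal capture gives no difference at any c. With a higher Tavanic rate, the shrinkage runs the other way.

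**The case against.** The strongest reply is that AE recording does not pass through the physical examination. Patients are in hospital and infusions are supervised. After the nemonoxacin bag at least another hour of supervised infusion follows, and the investigator or sub-investigator sees the patient for vital signs. AEs are documented each i.v. day, whether observed or reported. A reaction during a supervised infusion is easy to see. This stands: loss of events is a possibility, and the documents do not show that it happens. What remains is that no passage asks anyone to look for these reactions, so recording of mild ones can vary by site.

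A second reply is that Section 12.7 already counts by arm. This also stands. A reader might infer that infusion-site reactions and rash get no by-arm count; Section 12.7 contradicts that at both system organ class and preferred-term level. Only the grouped patient count and the phase split are absent. Section 12.9 leaves detail to a separate statistical analysis plan, where they could still be placed.

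A third reply is that the safety analysis is descriptive and the events are mild, so no test or decision depends on them. That limits the weight of the point but does not remove it, since the comparison is a stated objective.

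Finally, recording reactions bag by bag would give blinded site staff a cue to the arm, because active nemonoxacin is only ever in the first bag and Tavanic only in the second. The same investigators judge the primary endpoint. This objection is sound and shapes the fix. The between-arm comparison does not need bag attribution.

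**Conclusion.** The point holds in a limited form and is worth acting on. No skin or infusion-site check is scheduled after an infusion. No grouped by-arm count of infusion-site reactions or of rash/pruritus is prespecified, and AEs are not split by treatment phase. The safety population can lose a patient whose only infusion was stopped for a reaction.

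The size of the counting gap is illustrated by the 17-to-68 range above, which assumes 68 affected patients and four terms. The size of any capture loss is unknown: the 25% to 100% range and the Tavanic rate are assumptions.

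A reader might go further and conclude that these reactions are under-recorded and that this favours nemonoxacin. The documents do not support either step. They give no capture rate and no levofloxacin rate for these reactions. The gap between infusion and vital signs differs by arm, and so does the supervised time after the active bag, so even equal capture cannot be taken for granted.

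**What to change.** **In Section 12.7**, add two prespecified by-arm rows: patients with at least one infusion-site reaction, and patients with at least one rash/pruritus event, each with onset during i.v. therapy. List the grouped terms before unblinding. Use all patients who started any i.v. study infusion as the denominator. Show AE tables by phase of onset (i.v., oral, follow-up).

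**On the infusion record** that staff already complete, add one daily yes/no entry for infusion-site reaction and one for rash/pruritus. Complete both once, after the two infusions, and cover anything seen or reported since the first infusion began, so that reactions already cleared are included. Record maximum severity and onset time. Do not ask staff to assign the reaction to a bag; this protects site blinding.

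**Cost.** Two table rows, a phase split, and a slight data-entry burden. Over the usual 3 to 7 i.v. days this is 2 × 3 = 6 to 2 × 7 = 14 yes/no entries per patient, or 342 × 6 = 2,052 to 342 × 14 = 4,788 in all, plus severity and onset time where the answer is yes. Sample size, treatment and the primary analysis are unaffected.
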